#### G. Endpoints

Primary: Completion of final blood collection and GTT.

Secondary: Completion of PROMIS 10 Questionnaire.

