## Research Plan

### A. Specific Aim

The aim of this study is to assess the effects of 1,25(OH)2D3 on insulin secretion by the pancreas and glucose utilization by skeletal muscle as well as to determine the effects of 1,25(OH)2D3 on muscle strength in pre-diabetic subjects.

Hypothesis: 1,25(OH)2D3 will increase the rate of insulin secretion by pancreatic beta cells and improve glucose uptake in muscle, resulting in improved glucose homeostasis. Secondarily, 1,25(OH)2D3 will increase muscle strength.

Approach: This will be a double blind randomized control trial in pre-diabetic persons. Each participant will be randomly assigned to receive an oral tablet containing 0.25 µg 1,25(OH)2D3 or a placebo tablet for 8 weeks. Identical assessments will be performed both before and after the 8-week intervention period. These assessments will include the 2-hour glucose tolerance test (GTT) and muscle strength testing.

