## F. Statistics and Analyses

Power calculations for determining sample sizes were performed in JMP Pro 14 by using previously published variances on DI and  $\phi$  that describe beta cell function in pre-diabetic persons (Sathananthan et al. 2012) (Table 3).

Table 3: Power calculations for determining sample size

Parameter	Expected Outcome (mean $\pm$ sd)	Total Sample Size
DI	$1920 \pm 321$ ( $10^{-14}$ dl/kg/min $^2$ per pmol/l)	28
$\phi$	$63.8 \pm 7.5$ ( $10^{-9}$ min $^{-1}$ )	15
		47

\* Total N to detect a 20% difference with 85% power between two groups of N/2.

Analysis: Data will be analyzed as a repeated measures analysis of variance (ANOVA) with the independent variable as 1,25(OH) $_2$ D $_3$  or placebo and the dependent variable as assessments made before and after intervention. The main effect will be an analysis of the study groups pooled across gender and hormonal status to compare intervention with placebo. Additional co-variables to be considered in the analyses will be sex and menopausal stage per study group affiliation, as well as age, race, and others as post-hoc analyses.

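### The stated primary endpoint is completion of procedures, and no efficacy variable is named as primary anywhere in the plan

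*Combined protocol and SAP*

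**What the plan says.** Section G (Endpoints) is the only place that labels endpoints, and it has two entries: "Primary: Completion of final blood collection and GTT" and "Secondary: Completion of PROMIS 10 Questionnaire".

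Other sections describe a different trial:

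- Section A (Specific Aim) hypothesises that calcitriol "will increase the rate of insulin secretion by pancreatic beta cells and improve glucose uptake in muscle, resulting in improved glucose homeostasis", and as a second matter that it "will increase muscle strength".
- Section D (Study Design) sets out a before-and-after comparison of insulin secretion, glucose uptake and muscle function under calcitriol or placebo.
- Section F (Statistics and Analyses) bases the sample size on DI and phi, with the Table 3 footnote "Total N to detect a 20% difference with 85% power between two groups of N/2".
- The Section F analysis is a repeated measures ANOVA with "the dependent variable as assessments made before and after intervention". Its headline comparison reads: "The main effect will be an analysis of the study groups pooled across gender and hormonal status to compare intervention with placebo".

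The glucose tolerance test paragraph of Section E lists fasting, peak and nadir insulin, area measures, insulin action (Si), phi and DI, and ranks none of them.

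**The concern.** A participant who finishes the last glucose tolerance test counts the same under Section G whether glucose handling improved, worsened or did not change. The stated primary result therefore cannot answer the hypothesis. Muscle strength, the second hypothesis, does not appear in Section G at all.

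The efficacy comparison that is clearly intended has no named primary variable. Table 3 offers two candidates without ranking them or giving a multiplicity rule, and the glucose tolerance test yields several more. The deciding variable could be picked once results are known, and the trial would then have no prespecified confirmatory test. The blinding statement in the Study Intervention Agent section covers participants, care providers and staff with direct participant contact. It does not mention analysts, so it cannot be relied on to close the gap.

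**Working it through.** **1. What Table 3 powers.** Inputs from Table 3: DI mean 1920, SD 321; phi mean 63.8, SD 7.5; 20% difference, 85% power, two equal groups. Alpha is not stated and is taken as two-sided 0.05.

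Method: two-sample t test, standardised difference d = 0.2 × mean / SD, noncentrality d × √N / 2, with N − 2 degrees of freedom.

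- DI: 0.2 × 1920 = 384; d = 384 / 321 = 1.196. Smallest total N is 28 (power 86.1%).
- phi: 0.2 × 63.8 = 12.76; d = 12.76 / 7.5 = 1.701. Smallest total N is 15 (power 86.1%).

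Both match Table 3 exactly. Two-sided 0.01 would give 40 and 22, two-sided 0.10 would give 22 and 12, and one-sided 0.05 would give 22 and 12, so the assumed alpha is well supported. The sample size thus rests on mean differences in two continuous variables. The plan gives no expected completion rate, no difference in rates and no analysis of completion, so nothing in it powers or tests the Section G endpoints.

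**2. What leaving DI and phi unranked could cost.** This is an illustration: it supposes that a positive test on either variable at 0.05 counts as success, which no section states.

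- Independent tests: 1 − 0.95² = 0.0975.
- Bivariate normal, assumed correlation 0.5: 0.0907.
- Bivariate normal, assumed correlation 0.9: 0.0704.

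Naming one variable at 0.05 returns the figure to 0.05.

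**3. Whether naming one variable needs more participants.** The Human Subjects section plans 50 completers, 25 per group. With DI alone at two-sided 0.05 and Table 3's SD, power at N = 50 is 98.5%.

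Table 3 does not say whether its SD belongs to a single visit or to change. With two visits, the treatment-by-time test in the ANOVA is the t test on change. If 321 is a single-visit SD, the SD of change is 321 × √(2(1 − r)), where r is the before-after correlation. The documents do not give r, so a range is shown:

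| Assumed r | SD of change | N for 85% power | Power at N = 50 |
|---|---|---|---|
| 0 | 454 | 53 | 83.4% |
| 0.05 | 442 | 50 | 85.2% |
| 0.1 | 431 | 48 | 87.1% |
| 0.5 | 321 | 28 | 98.5% |

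Power at 50 reaches 85% at r of about 0.044. The 53 at r = 0 is an odd number; equal groups would need 54.

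**The case against.** The strongest reply is that Section G was meant to mark when a participant has finished the study. Its wording fits the final visit in Table 2, which lists the same blood draw, glucose tolerance test and questionnaire. On that reading the section is mislabelled, and the intended outcomes can largely be inferred: the glucose tolerance test is the source of DI and phi, Table 3 sizes the trial on those two alone, Section A puts strength second, and Section F fixes a pooled comparison of calcitriol with placebo.

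Much of this is fair. It narrows the main ambiguity to DI versus phi. But the text does not say that Section G marks the end of participation, and if it does, the protocol has no labelled efficacy endpoint at all. Inference from Table 3 still leaves two unranked candidates.

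Three lesser points stand:

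- The type I error figures depend on a success rule the plan does not contain, so they illustrate a risk and are not an error rate of this plan.
- Silence about analysts does not show that they are unblinded.
- The choice of DI over phi is open to argument. Phi measures secretion directly, secretion comes first in the hypothesis, and phi has the larger standardised difference (1.701 against 1.196).

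**Conclusion.** The concern holds and should be fixed before analysis. Section G names procedural events as primary and secondary endpoints, these do not measure the hypothesis or match what Table 3 powers, and no section names a primary efficacy variable. This rests on the text alone. It does not depend on the illustrative type I error of 7.0% to 9.75%, nor on what the authors meant Section G to do.

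The statement that no added participants are needed is conditional. It assumes two-sided 0.05 and Table 3's mean, SD and 20% effect. If that SD is a single-visit SD and change is analysed, it also needs a before-after correlation of about 0.044 or more.

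**What to change.** Before anyone, analysts included, sees data by arm, replace the Section G primary with one variable that Table 3 already powers, and name the same variable in Section F. For example: the between-arm difference in change in DI from baseline to week 8, tested as the treatment-by-time contrast of the Section F ANOVA at two-sided alpha 0.05.

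- **Choice of variable.** DI is a reasonable candidate because DI = phi × Si covers both secretion and insulin action. It cannot separate the two, so phi and Si should come first among the secondary variables. The sponsor may prefer phi; what matters is that one is fixed in advance. Section E refers to responsivity indices in the plural, so the text should say which phi index is used, alone or within DI.
- **If both are wanted as primary.** Testing each at two-sided 0.025 needs 33 participants for DI and 18 for phi on Table 3's inputs. Power at 50 completers is then 97.0% and 99.98%.
- **Other outcomes.** List the remaining glucose tolerance indices, knee-flexor torque, grip strength and the PROMIS 10 score as secondary or exploratory.
- **Completion.** Keep it as a feasibility descriptor, or retitle Section G if it was meant to mark the end of participation.

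The cost is protocol wording only, subject to the power condition in the verdict. The documents do not show the trial's status; if data by arm have already been seen, the choice must be reported as post hoc.

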### Human Subjects

#### Risks to the subjects

Human Subjects Involvement and Characteristics: All protocols and all techniques to be used will be approved by the Mayo Clinic Institutional Review Board (IRB) prior to initiation of any studies. Subject characteristics and inclusion/exclusion criteria have been clearly specified above. Our plan is to complete the study on 50 participants with 25 in each group. We are anticipating a target accrual of 75 subjects to account for anticipated dropout in order to have 50 participants complete the study.

Sources of Materials. Samples of blood and urine obtained during the study will be used exclusively for research purposes. No use will be made of pre-existing specimens.

Urine: Urine samples will be collected from women for pregnancy testing.

Blood: One blood draw will occur during the screening visit (approximately 15 mL). A glucose tolerance test will be performed at baseline that will include seven blood draws (approximately 1 mL of blood from each draw) periodically over the course of 2 hours. Every 2 weeks during the intervention, a small sample of blood (1 mL) will be collected to monitor calcium and phosphorus levels. At completion of 8 weeks of intervention, another GTT will be performed and 5 mL of blood will be collected for post-intervention analysis. This analysis will include calcium, phosphorus, 25(OH)D $_3$ , 25(OH)D $_2$ , 1,25(OH) $_2$ D $_3$ , and 1,25(OH) $_2$ D $_2$ . All specimens will be processed internally and stored in the study team laboratory.

#### Potential Risks:

The following are potential risks for this study

- a) Blood will be withdrawn. The total blood withdrawn throughout the 8-week study will be approximately 40 mL.
- b) The study agent, 1,25(OH)2D3, has potential risks that are considered rare at the dosage in use. These risks include hypercalcemia, hyperphosphatemia, weakness, headache, nausea, vomiting, sleepiness, dry mouth, constipation, muscle pain, bone pain, or a metallic taste.

#### Adequacy of Protection Against Risks

Feasibility, Recruitment, and Informed Consent: Volunteers will be initially recruited from individuals who have previously indicated a desire to participate in research. Each willing participant will meet one of the investigators who will explain the scientific rationale, the procedures and the potential risks involved in the study. The consent form will be approved by the Mayo Clinic IRB prior to use. Informed written consent from the participant will be obtained by one of the investigators prior to participation. An electronic note will be entered in each participant's medical record regarding the consent and a copy of the consent will be electronically kept with the participant's medical record. A copy of the consent will be offered to the subject and the original kept with the investigators records.

Protection against risk: All protocols and all techniques to be used will be approved by the Mayo Clinic IRB prior to initiation of any studies. All participants will have the Mayo Clinic paging operator available to them 24 hours a day to contact the investigators for any problems. The Clinical Research and Trials Unit (CRTU) also has an on-call physician available 24 hours a day to contact for problems or concerns in the event that the study MD does not respond to calls or pages. The following protection will be taken for the risks identified above:

- a) The amount of blood drawn is within the amounts acceptable by the institution. There is an institutional electronic tracking system to ensure that a patient is not in more than one study at a time.
- b) A Data Safety and Monitoring Plan (DSMP) will be utilized for patient safety. Investigators and the CRTU have had extensive experience in all procedures and aspects of the study. The investigative team will review any participant safety issues as delineated in the DSMP.
- c) Subject protection is as listed in the above section. Confidentiality of all medical records is strictly maintained by established procedures. The original study data are kept in the Principal Investigator's laboratory/office and are entered into a secure Mayo firewall allocated for use by only the study team. All data are reviewed by the Principal Investigator. All investigators carry pagers. Volunteers have access to the Mayo Clinic paging operator 24 hours a day.
- d) The risks to the subjects are small being primarily those of blood withdrawal.
- e) Participants will have their serum calcium and phosphorus levels repeatedly checked following administration of 1,25(OH)2D3 or placebo. Participants who develop an increase in their calcium or phosphorus level above the institutional upper limit of normal (defined values) will be taken off the intervention, referred to their primary healthcare provider, and have their blood calcium and phosphorus reassessed after two weeks or until the concentrations return to within normal limits.

#### Potential Benefits of Proposed Research to the Subjects and Others

Evidence for the impact of 1,25(OH)2D3 on glucose metabolism and muscle function is steadily increasing. When administered in low doses, this treatment may be a reliable option that is currently

approved by the US Food and Drug Administration, for improving glucose metabolism in persons who are prone to T2DM. Participants included in this study may experience benefits that could enhance their general health and fitness and prevent development of T2DM.

### Protection of Human Research Participants

The personnel identified in the application have completed the required education on the protection of human research participants. The institution has established a formal program entitled the Mayo Investigator Training Program (MITP). The MITP is a web-based educational course designed to provide all personnel involved in human subjects research with training about human subject protection. All Mayo personnel engaged in human subject research are required to complete the course and recertify themselves every two years. The primary objectives of the course are to provide the historical framework for current human subject protection regulations and to explore the evolving issues related to human subject research. The course is divided into four sections:

1. Course introduction and general overview
2. History section which explores examples of unethical behavior in human subject research
3. Review of major human subject protection issues
4. Discussion of the various roles and responsibilities of individuals involved in human subject research.

At the conclusion of the instruction, individuals are required to complete a thirty-question assessment.

